### Hypothesis

Early corticosteroids will improve survival (Early Cohort) in patients with AHRF; and extending corticosteroids (Extended Cohort) will improve survival in those with AHRF still requiring invasive or non-invasive respiratory despite already receiving approximately 10 days of corticosteroids.

[figure not shown]
### The CORT-E2 Study Outcomes

#### Primary Outcome

60-day mortality from the day of randomization

[figure not shown]
#### Secondary Outcomes

1. Mortality at other endpoints (ICU/hospital discharge, 30 days and 6 months)
2. Hospital length of stay
3. Duration of NIV
4. Duration of supplemental oxygen use
5. Ordinal scale of daily respiratory support\*\*
6. Need for ECLS
7. Duration of ECLS (for those that require ECLS)
8. Ventilator-free days (VFDs) censored at day 30
9. Health-related quality of life at 6 months (measured with EQ-5D)
10. *Complications from Corticosteroids:*
  - a. Hyponatremia (serum sodium > 150 mmol/L)

- b. Hyperglycemia (requiring new insulin or increase in insulin by >30% from initial/baseline dose)
- c. Delirium
- d. Clinically important GI bleeding (requiring endoscopy or RBC transfusion)
- e. Nosocomial infection
- f. Neuromuscular weakness

\*\*The daily respiratory support ordinal scale will use longitudinal proportional odds to categorize each patient's daily respiratory support needs for 30 days. Each patient will be assigned one of the following ordinal categories each day: 6 (no support), 5 (supplemental oxygen), 4 (high flow nasal cannula), 3 (non-invasive ventilation), 2 (invasive mechanical ventilation), 1 (extracorporeal life support), 0 (death). We will assess daily respiratory support needs using Markov longitudinal proportional odds modelling to estimate an odds ratio. This represents a novel scale that will be assessed compared to the other patient-important outcomes listed above.

---

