## Why This Study Is Needed

This clinical trial is designed to inform clinical practice and address two knowledge gaps in COVID and non-COVID respiratory failure.

**Early Cohort** – *There is uncertainty whether lessons learned from corticosteroids in COVID AHRF are generalizable to non-COVID AHRF.* The DEXA-ARDS trial randomized 277 critically ill patients with non-COVID ARDS to receive dexamethasone 20mg daily or placebo and found a reduction in mortality (-15.3%, 95% CI -4.9 to -25.9%) and an increase in ventilator-free days at 28 days (MD 4.8 days more, 95% CI 2.57 to 7.03 days more) with dexamethasone. A 2015 meta-analysis suggested that corticosteroids reduced mortality in patients with severe community-acquired pneumonia (RR 0.67, 95% CI 0.45 to 1.01). Despite these data suggesting benefit of corticosteroids in non-COVID AHRF, use of this therapy remains highly variable. The 2017 Society of Critical Care Medicine (SCCM) guidelines made a conditional recommendation for corticosteroids in both ARDS and CAP based on moderate certainty evidence, with a rationale that further high quality data was needed before a strong recommendation could be made.

***Patients with non-COVID AHRF, not meeting traditional ARDS criteria, but receiving HFNC or NIV may benefit from corticosteroids but have not been sufficiently studied.*** Use of HFNC has increased markedly in patients with AHRF. In fact, the most recent 2020 European guideline made a strong recommendation for HFNC in patients with AHRF. We are aware of planned updates to the ARDS definition that will include patients on HFNC. Studies evaluating the effect of corticosteroids in critically ill COVID patients demonstrated a trend towards greater effect of corticosteroids in those requiring HFNC or NIV compared to invasive mechanical ventilation (ratio of ORs 4.34, 95% CI 1.46 to 12.91) with the hypothesis that modulating the inflammatory response early before it becomes too severe may be optimal. Corticosteroids also reduce the need for invasive mechanical ventilation in patients with COVID AHRF (25 fewer per 1000, 95% CI 1 to 44 fewer). It is unclear whether these lessons learned from COVID AHRF are generalizable to non-COVID AHRF patients on HFNC or NIV.

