### Patient Population

The CORT-E trial is a phase III, multi-centre (30-40 centres), randomized, open-label trial, embedded as a domain within the PRACTICAL platform trial. This domain will enrol patients in the following platform defined states (in both trial cohorts);

[figure not shown]
- Non-intubated patients;
- Intubated patients, not on extracorporeal life support, with low normalized respiratory system elastance (<2.5 cm H2O/ml/kg predicted body weight);
- Intubated patients, not on extracorporeal life support, with high normalized respiratory system elastance (≥2.5 cm H2O/ml/kg predicted body weight);
- Patients on extracorporeal life support.

Patients who satisfy the PRACTICAL platform eligibility criteria **and** the criteria specific to **either** cohort in the CORT-E domain will be considered.

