corticosteroid prescription (e.g., if only 8 or 9 days were prescribed) or practicalities (e.g., to avoid weekends or holidays). If there is uncertainty as to whether corticosteroids were prescribed for AHRF or another indication, the treating team should be consulted to confirm eligibility.

Sites will maintain a screening log documenting all patients reviewed and reasons for exclusion.

Eligible and consented patients for either cohort will be randomized via REDCap, following a 1:1 (intervention arm: control arm) schedule stratified by study centre and level of oxygen support (non-invasive, invasive or ECLS) at the time of randomization.

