## TRIAL INTERVENTIONS

### Early Cohort

#### Intervention Arm:

[figure not shown]
Patients randomized to receive corticosteroids will receive dexamethasone 20mg daily for 5 days and then 10mg for an additional 5 days, for a total of 10 days or until ICU discharge or death, whichever comes first. After 10 days dexamethasone will be stopped without a taper. If a patient is discharged from the ICU prior to completing the protocol, then ongoing corticosteroid management will be up to the treating team as per SOC.

Dexamethasone will be administered parenterally (intravenous administration). Specific details on the timing of administration are provided below;

- 20mg dexamethasone is to be administered as soon as possible and on the day of randomization (Day 0), and this dose will be administered daily for a total of 5 days of treatment (Day 0 – Day 4). Then, the dexamethasone dose will be reduced to 10mg and this dose will be administered daily for a total of 5 days (Day 5 – Day 9).
- In rare cases where it is not possible to administer the first dose of study drug on the same day as randomization (e.g., if the patient is randomized very close to midnight), 20 mg dexamethasone can be started the day following randomization (Day 1), and will be administered daily for a total of 5 days of treatment (Day 1 – Day 5). Then, the dexamethasone dose will be reduced to 10mg and this dose will be administered daily for a total of 5 days (Day 6 – Day 10).

Patients finishing 10 days of dexamethasone as part of the Early Cohort will be eligible for randomization in the Extended Cohort if they are still requiring HFNC, NIV, IMV or ECLS, and according to the other eligibility criteria for the Extended Cohort.

**Control Arm:** Those randomized to usual care will receive routine AHRF management without corticosteroids. All other aspects of care will be at the discretion of the treating team including antibiotics, intravenous fluids, mechanical ventilation and ECLS.

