### **Analyses**

Any deviation from the original statistical plan will be described in the final report.

[figure not shown]

All analyses, interim and final, will use the intention-to-treat principle. The baseline characteristics comparing randomized groups will be reported using means (and standard deviations), medians (and interquartile ranges) or proportions. Trial data will be analyzed using Bayesian hierarchical generalized linear models to estimate the posterior probability of superiority (or inferiority) and equivalence for each intervention within each domain. The hierarchical model will account for centre, time period, sex and oxygen support at the time of randomization (HNFC, NIV, invasive mechanical ventilation or ECLS). Posterior probability distributions will be computed by combining the likelihood function with minimally informative priors and updated every three months as information (observations) accumulate in the trial. Statistical analysis will be adjusted for whether a patient was enrolled in one CORT-E cohort or both CORT-E cohorts. We do not expect interaction between CORT-E and the other PRACTICAL domains. The final study analysis, separate for each cohort, will be completed once either superiority, inferiority or equivalence has been observed and confirmed by the DSMB and Platform Steering Committee.

We will collect sex and perform subgroup analysis based on this variable. It is less feasible to collect gender as most patients will not be conscious at the time of enrolment. We don't expect effect modification for either cohort based on sex or gender. Understanding the CORT-E eligibility criteria, we plan to enroll a diverse population of patients representative of the demographics of ICU patients presenting at the participating sites.

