### **MINIMIZING SOURCES OF BIAS**

The online randomization system will ensure allocation concealment and employ variable block sizes. Patients and treating healthcare providers will not be blinded. While blinding is an important mechanism to mitigate performance and detection bias, blinding would not allow for subsequent randomization of those that receive dexamethasone in the Early Cohort to further randomization in the Extended Cohort, thereby eliminating our efficiency and ability to answer multiple questions within the same trial. We will mitigate outcome ascertainment bias by using relatively objective outcomes not easily influenced by knowledge of treatment assignment (e.g. mortality). We will blind data analysts and statisticians. For the few subjective outcomes (e.g., nosocomial infections), we will establish a blinded adjudication committee that will evaluate events using standardized and accepted definitions to limit risk of bias.

We will collect data related to co-interventions to evaluate whether lack of blinding leads to differential use of specific interventions or treatments and will provide protocols for ventilation, and supportive therapy best practices to help ensure consistency. We will also minimize bias by using an intention-to-treat analysis and minimizing loss to follow-up. Missing data will also be minimized through use of a clear and comprehensive data dictionary with online data entry using logical consistency rules.

---

---

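### Secondary outcome 7 (ECLS duration among those who require ECLS) pools patients on ECLS at randomisation with patients who start it later, so a between-arm difference in duration can mislead

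*Protocol*

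**What the plan says.** - **The outcome.** In the protocol's Secondary Outcomes, item 7 is "Duration of ECLS (for those that require ECLS". The Synopsis repeats it. Item 6, directly above, is the need for ECLS.
- **Who can be in the group.** Patient Population lists "Patients on extracorporeal life support" among the enrolled states. Patient Randomization says that allocation is "stratified by study centre and level of oxygen support (non-invasive, invasive or ECLS) at the time of randomization".
- **Who decides on ECLS.** For the Early Cohort control arm, Trial Interventions says "All other aspects of care will be at the discretion of the treating team including antibiotics, intravenous fluids, mechanical ventilation and ECLS". The Extended Cohort text likewise leaves other care to the treating team. Minimizing Sources of Bias says "Patients and treating healthcare providers will not be blinded".
- **Expected effects.** The Hypothesis begins "Early corticosteroids will improve survival (Early Cohort) in patients with AHRF" and says the same of extended treatment. Why This Study Is Needed reports, for a neighbouring step of support, "Corticosteroids also reduce the need for invasive mechanical ventilation in patients with COVID AHRF (25 fewer per 1000, 95% CI 1 to 44 fewer" (the parenthesis closes there). That evidence concerns invasive ventilation, not ECLS.
- **Analysis principle.** Analyses states "All analyses, interim and final, will use the intention-to-treat principle".
- **What else covers ECLS.** Item 5 scores every patient daily for 30 days on a scale in which ECLS and death are the two lowest categories.

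**The concern.** The restriction to ECLS users is part of the outcome definition, so it is a stated choice and not a detail left open. For patients not on ECLS at randomisation, membership of the group is settled after randomisation, by an event that item 6 treats as something corticosteroids may change.

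If dexamethasone spares some patients ECLS, those who still receive it in the treated arm are not the counterparts of the control users. If the spared cases would have had short runs, the remainder has longer ones and treatment looks as if it prolongs ECLS. Knowledge of the arm can also influence who is put on ECLS.

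At stake is a named secondary result that could be read as harm when the total burden of ECLS has fallen, or as benefit for the wrong reason.

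**Working it through.** The protocol gives no ECLS rate, duration or standard deviation, so there is no stated figure to reproduce. The calculations use assumed inputs and show only which way the comparison can move.

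**Illustration 1: later starters only.** Assume that 5% of controls need ECLS, half for 7 days and half for 14, and that treatment does not change the length of any given run. Let m be the share of control-arm cases that are mild and still occur under treatment (0.5 under control).

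- Mean among users = (m×7 + 0.5×14)/(m + 0.5)
- ECLS days per 100 randomised = 5×(m×7 + 0.5×14)
- Control, m = 0.5: 10.5/1.0 = 10.5 days; 5×10.5 = 52.5 days per 100
- 20% of cases prevented, all mild, m = 0.3: 9.1/0.8 = 11.4 days; 5×9.1 = 45.5 per 100
- 50% prevented, all mild, m = 0: 7.0/0.5 = 14.0 days; 5×7.0 = 35.0 per 100

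Users look worse by 0.9 to 3.5 days while the burden falls by 7.0 to 17.5 days per 100.

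The direction depends on which cases are prevented. If the 20% prevented were all long runs, the mean among users would be (0.5×7 + 0.3×14)/0.8 = 7.7/0.8 = 9.6 days, an apparent shortening although no run became shorter. If mild and long cases were prevented in equal proportion, the mean would stay at 10.5.

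**Illustration 2: adding patients on ECLS at randomisation.** Assume that a share b of all patients is on ECLS at baseline (mean 12 days) and that a further 10% of controls start it later. A fraction f of these starters are milder (7 days) and are all spared by treatment; the rest have 14 days.

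- Control mean among users = [12b + 0.10×(7f + 14(1−f))]/(b + 0.10)
- Treated mean among users = [12b + 0.10×14(1−f)]/(b + 0.10(1−f))

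Example, b = 5%, f = 25%: control (0.6 + 1.225)/0.15 = 12.17; treated (0.6 + 1.05)/0.125 = 13.20; difference +1.03 days.

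Treatment minus control among users, in days, with no change in run length:

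| b | f = 10% | f = 25% | f = 40% |
|---|---|---|---|
| 0 | +0.70 | +1.75 | +2.80 |
| 5% | +0.42 | +1.03 | +1.62 |
| 10% | +0.30 | +0.73 | +1.15 |

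Mean ECLS days over all randomised patients (0 if never on ECLS) change by −0.10×7f, that is −0.07, −0.175 and −0.28 days, whatever b is.

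The same differences among users if treatment also shortens every run by 10% (treated mean × 0.9):

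| b | f = 10% | f = 25% | f = 40% |
|---|---|---|---|
| 0 | −0.70 | +0.35 | +1.40 |
| 5% | −0.91 | −0.29 | +0.32 |
| 10% | −1.00 | −0.55 | −0.13 |

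Baseline ECLS patients dilute the distortion. With a real shortening, the sign is wrong in three of these nine cases and right in the other six. The all-patient difference favours treatment in all nine.

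**The case against.** The strongest reply has four parts.

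1. **Part of the group is randomised.** Patients on ECLS at randomisation are enrolled and stratified, and ECLS at baseline is a planned subgroup. A reader might infer that the whole item 7 comparison is non-randomised. The documents do not support that: only the later starters raise the problem. Because item 7 does not separate the two groups, the pooled comparison still inherits it.

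2. **Item 7 is an outcome label.** It gives no model and no rule for death on ECLS, and a statistical analysis plan may settle both. A reader might infer that death on ECLS counts as a favourable short duration. That would follow if a run simply ended at death, but the protocol does not say so. What stands without it is the restriction to users, which is written into the definition. The label is also compatible with purely descriptive reporting.

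3. **Intention to treat.** A reader might infer that item 7 breaches the statement "All analyses, interim and final, will use the intention-to-treat principle". Nothing in item 7 moves patients between arms or groups them by treatment received. The issue is which patients the outcome is defined for. The two texts sit uneasily together, but it should not be called a breach.

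4. **Other outcomes limit the harm.** Items 5 and 6 cover all patients and would show a reduction in ECLS use. The stopping triggers in Sample Size use 60-day mortality only.

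The illustrations are also wholly assumed, and removing only milder cases is the pattern that most favours the apparent lengthening. All four parts narrow the point. None makes the between-arm comparison among later starters valid.

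**Conclusion.** The point holds in a limited form. For patients who start ECLS after randomisation, a between-arm comparison of duration conditions on an event that treatment may change and that unblinded clinicians decide. Pooling them with patients already on ECLS weakens the distortion but does not remove it.

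The size cannot be stated. Under the assumed inputs, and with no effect on run length, the spurious lengthening is 0.3 to 3.5 days across the two illustrations. It would vanish if the cases prevented were unrelated to expected duration, and reverse if they were mainly long runs. The conclusion is that the result can mislead, not that it must.

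This concerns one secondary outcome. It does not touch the primary outcome or the stopping rules.

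**What to change.** - **Between-arm comparison on all randomised patients.** Use ECLS-free days to day 30, with death as the worst value and patients never on ECLS given the full number of days. Alternatively, use days alive and on ECLS (0 if never used), read alongside mortality because early death also lowers that count.
- **Duration among users** stays as description only, with no inference between arms.
- **Any randomised comparison of duration** is confined to patients on ECLS at randomisation, with an explicit rule for death.

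**Cost.** A few lines of outcome wording in Secondary Outcomes and the Synopsis. No new data are needed: daily data run through the ICU stay up to day 30, ECMO is documented, and the daily scale already records ECLS and death.

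**Downside.** ECLS-free days will have many patients at the ceiling and will be driven largely by mortality. The protocol's background gives mortality of 20% to 50%, against the 5% ECLS use assumed in the first illustration. The outcome therefore overlaps with items 1 and 5 and says less about duration itself, which is a reason to keep the descriptive summary.

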
Domain Secondary Outcome:
	
 
1. Mortality at other endpoints (ICU/hospital discharge, 30 days and 6 months)
 
2. Hospital length of stay
 
3. Duration of NIV
 
4. Duration of supplemental oxygen use
 
5. Ordinal scale of daily respiratory support
 
6. Need for ECLS
 
7. Duration of ECLS (for those that require ECLS)
 
8. Ventilator-free days (VFDs) censored at day 30
 
9. Health-related quality of life at 6 months (measured with EQ-5D)
 
10. Complications from Corticosteroids: 
 
a. Hyponatremia (serum sodium > 150 mmol/L)
 
b. Hyperglycemia (requiring new insulin or increase in insulin by >30% from initial/baseline dose)
 
c. Delirium
 
d. Clinically important GI bleeding (requiring endoscopy or RBC transfusion)
 
e. Nosocomial infection
 
f. Neuromuscular weakness
 
 
 

Domain Design:
	
A phase III, interventional, open-label, randomized, multi-site study

Duration:
	
2.5 years of accrual and 6 months follow-up for a total study duration of approximately 3 years.

Planned Total Sample Size:
	
The Bayesian approach does not require a fixed sample size as the trial will continue enrolling until a statistical trigger is met (see section Sample Size for additional details). It is estimated that a maximum of 2000 patients will be enrolled in each cohort at 30 to 40 sites.

Inclusion/Exclusion Criteria:	
Patients will be eligible for enrolment in this domain if they meet the PRACTICAL platform eligibility criteria and the criteria specific to either cohort in the CORT-E domain.
 
PRACTICAL Inclusion Criteria
 
1) Acute hypoxemic respiratory failure meeting all of the following criteria;
 

a) New or worsening respiratory symptoms developing within 2 weeks prior to the onset of need for oxygen or respiratory support

b) Receiving any of the following types of oxygen or respiratory support for at least 4 hours prior to the time of randomization; supplemental oxygen at 10 L/min or higher, high flow nasal oxygen (at any flow rate),

--------------------------------------	--

[figure not shown]

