**Study Assessment Schema**

Required Investigations*	Baseline	Daily**	D3	D7	D28 or ICU DC 	D60 	6 Months 
Window	Within 72 hours prior to randomization	N/A	N/A	N/A	N/A	+10 days	+/- 14 days
Consent  & Randomization	X						
Demographics 	X						
Medical History 	X						
Vitals 	X	X					
Hemodynamics 	X	X					
Hematology 	X	X					
Biochemistry 	X	X					
Arterial Blood Gases (ABG) 	X	X					
Study Drug Administration	Refer to the 'TRIAL INTERVENTIONS' section for details related to each cohort						
Optional: Blood Sample Collection	X		X	X	X		
Mechanical Ventilation Data		X					
Readiness to Wean	X	X					
Spontaneous Breathing Trial		X 					
EQ-5D-5L							X

Glasgow Coma Scale and Sofa Score	X	X					
Vital Status						X	X
Serious Adverse Events		X 					
Concomitant Medications		X					

 Consent should be done prior to any baseline assessments and according to site institutional timelines. Site should follow their institutional guidelines for consenting window (timeframe for prior to enrollment/protocol treatment). Please refer to section “Patient population, eligibility and enrollment”.

 Demographics include age, gender, height, and weight.

 Hospital admission (date/time), ICU admission (date/time), APACHE IV, Charlson Comorbidity Index, COVID-19 infection status

 Vitals include temperature, heart rate, respiratory rate, and blood pressure.

 Hemodynamics include BP, PCWP, SvO2

 If multiple time points for baseline data are available within the time point window, values closest to randomization should be entered.

 Hematology reporting on Hg, WBCs, and platelets.

 Biochemistry will include reporting the following values: sodium, glucose, creatinine, albumin, bilirubin, potassium, bicarbonate.

 ABG testing will include the following parameters: pH, PaCO2, HCO3, SaO2, lactate, hemoglobin.

 Spontaneous breathing trials will be conducted only when patient is deemed ready for weaning and per standard of care and/or institutional guidelines.

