 SAEs will be reported at the start of randomization and for a period of up to 30 days, or while in ICU, whichever is shorter.

 EQ-5D-5L administered via phone or e-mail at 6 months.

[figure not shown]
 The timing of the D60 and 6 Month follow-up are based on calendar days from the day of randomization (D0). The second randomization date (Extended Cohort randomization) will be used as the starting point for this follow-up for patients randomized into both the Early Cohort and Extended Cohort. These patients do not have to have these follow-up assessment’s done twice.

 The Day 60 vital status check can be done based on review of medical records if the site has access. In those cases, it is not necessary to contact the patient.

 Day 28 or ICU discharge (DC) (whichever is sooner)

[figure not shown]
\*All highlighted and blue fields are standard-of-care assessments and data being collected for study purposes.

\*\*Daily data common to all groups will be collected for the duration of ICU stay and up to day 30 (no daily data will be collected on the ward).

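### Secondary outcome 10a contradicts itself: it is labelled hyponatremia but defined as serum sodium above 150 mmol/L

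*Protocol*

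**What the plan says.** The protocol's Secondary Outcomes section ends with item 10, headed "Complications from Corticosteroids", which has six components, a to f. The first, 10a, reads "Hyponatremia (serum sodium > 150 mmol/L". The list in the Synopsis uses the same label, "Hyponatremia (serum sodium", followed by the same direction and the same value, above 150 mmol/L.

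The data behind the outcome are set out in the Study Assessment Schema. The biochemistry footnote states: "Biochemistry will include reporting the following values: sodium, glucose, creatinine, albumin, bilirubin, potassium, bicarbonate". Biochemistry is marked at baseline and daily. On duration, the schema says: "Daily data common to all groups will be collected for the duration of ICU stay and up to day 30". It adds that daily collection does not continue on the ward.

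**The concern.** Hyponatremia is low serum sodium. A value above 150 mmol/L is high serum sodium, which is hypernatremia. The name and the criterion of this prespecified outcome therefore point to opposite disorders, and a reader has to discard one of them to use the item.

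What is at stake is a safety result. Applied as written, the number produces a count of high-sodium events that would be tabulated and published as hyponatremia. Applied by name, the outcome becomes a count of low-sodium events with no threshold in the protocol to define them.

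The item 10 list also matters more here than in many trials. Under Safety and Reporting Requirements, generic adverse events are not collected. Under Serious Adverse Event, an event qualifies only if the attending physician believes it is related to the study drug. The listed complications are therefore an important part of the comparison of harms between arms.

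**Working it through.** No arithmetic applies. The protocol states no figure that depends on this item. The check is a comparison of the relevant texts.

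1. **Label against criterion.** Secondary Outcomes, item 10a: the label is low sodium and the criterion is serum sodium > 150 mmol/L. A measurement above 150 meets the criterion and not the label. A low measurement meets the label and not the criterion. No single measurement can meet both.

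2. **Main text against Synopsis.** The label, the direction of the inequality and the value are the same in both places. A fault in converting the PDF is therefore very unlikely. Both places are current protocol text, not a record of superseded wording.

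3. **Search for a passage that resolves it.** No other section defines the outcome, gives a lower sodium threshold or uses the word hypernatremia. Safety of Intervention discusses metabolic derangements but names no sodium disorder. The contradiction stands unresolved in the protocol.

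4. **Which half is likely to be the slip.** The criterion is specific and appears twice unchanged. The name alone cannot be applied, because no low-sodium cut-off is given anywhere. Both facts suggest that the label is wrong and the number is right. This is an inference, because the protocol does not confirm it.

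5. **What can be recovered.** Sodium is recorded as a value at baseline and daily in the ICU up to day 30. Either definition can be computed from those values for that period. Neither can be computed from daily data after transfer to the ward.

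6. **What the item touches.** The primary outcome is 60-day mortality. The three stopping triggers and the sample-size simulations (Sample Size) rest on the odds ratio for that outcome. The subgroup analyses (Analyses) are limited to the primary outcome. Item 10a enters none of these.

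**The case against.** The best defence is that the criterion is explicit and can be applied. An analyst who uses > 150 mmol/L obtains one well-defined count, and only the heading above it is wrong. On this view it is a one-word slip that daily numeric sodium makes harmless. Much of that stands: the data are not lost and the likely intent can be guessed. It does not remove the error, because a prespecified harm would still be reported under the name of its opposite. The unseen SAP is no answer either. If it copies the protocol it inherits the contradiction, and if it corrects it the two documents disagree.

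Four stronger readings are tempting, but the protocol does not support them.

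- A reader might infer that sites will record events in both directions and make the outcome uninterpretable. No case report form is shown, and no section says that sites classify sodium events. The schema asks for the sodium value itself.
- A reader might infer that item 10 is part of the only safety data collected in both arms. The Synopsis and Evaluation of Safety both say that serious adverse events are recorded in both groups, and mortality is also collected in both. What can fairly be said is narrower: control patients are assigned no study drug, so serious adverse events that count only when related to it give a poor comparison between arms.
- A reader might infer that the two definitions can share no patients. That is true of a single measurement, but one patient could have low sodium on one day and high sodium on another.
- A reader might treat this as a debatable design choice. Nothing suggests that anyone chose it. It is an internal contradiction.

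**Conclusion.** The item is wrong as written. Secondary outcome 10a names one condition and defines the opposite one, in both places where it appears, and the protocol offers nothing to reconcile them.

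The size is limited: one component of six within one secondary outcome, with no bearing on the primary analysis, stopping or sample size, and recoverable from recorded sodium for the ICU stay up to day 30. It should still be corrected before analysis and reporting, because it is an operative safety definition and the mislabelled result could reach publication.

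The contradiction itself rests on no assumption beyond the meaning of the word. The view that the label is the faulty half is an inference from the repeated threshold and the absence of any low-sodium cut-off. It needs the sponsor's confirmation.

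**What to change.** 1. The sponsor confirms which condition was intended.
2. If the label is the slip, as seems likely, item 10a is changed to *Hypernatremia (serum sodium > 150 mmol/L)* in both the Synopsis and Secondary Outcomes. If low sodium was intended, the threshold must be replaced instead.
3. Any case report form or SAP text that repeats the item is checked and aligned.
4. The outcome is derived from the daily sodium values in the database, so that it does not depend on how anyone read the label. The report states that it covers the ICU stay up to day 30.

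The cost is one word in two places, a check of dependent documents, and a simple derivation. No new data are needed. Step 4 is a preference rather than a necessity, since correcting the label alone removes the contradiction.
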